6.4.1 Definition of adverse events

An AE is the development of an undesirable medical condition or the deterioration of a pre-existing medical condition following or during exposure to a pharmaceutical product, whether or not considered causally related to the product. An undesirable medical condition can be symptoms (eg, nausea, chest pain), signs (eg, tachycardia, enlarged liver) or the abnormal results of an investigation (eg, laboratory findings, ECG). In clinical studies, an AE can include an undesirable medical condition occurring at any time, including run-in or washout periods, even if no IP has been administered.

The term AE is used to include both serious and non-serious AEs.

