The Investigator will assess causal relationship between IP and each AE, and answer “yes” or “no” to the question “Do you consider that there is a reasonable possibility that the event may have been caused by the IP?”

For SAEs causal relationship will also be assessed for other medication and study procedures. Note that for SAEs that could be associated with any study procedure the causal relationship is implied as “yes”.

A guide to the interpretation of the causality question is found in [Appendix B](#) to the CSP.

Adverse Events based on signs and symptoms

All AEs spontaneously reported by the healthy volunteer or reported in response to the open question from the study personnel: “Have you had any health problems since you were last asked?”, or revealed by observation will be collected and recorded in the CRF. When collecting AEs the recording of diagnoses is preferred (when possible) to recording a list of signs and symptoms. However, if a diagnosis is known and there are other signs or symptoms that are not generally part of the diagnosis, the diagnosis and each sign or symptom will be recorded separately.

Adverse Events based on examinations and tests

The results from protocol mandated laboratory tests and vital signs will be summarised in the Clinical Study Report (CSR). Deterioration as compared to baseline in protocol-mandated laboratory values, vital signs, ECGs, and other safety assessments should therefore only be reported as AEs if they fulfil any of the SAE criteria.

If deterioration in a laboratory value or vital sign is associated with clinical signs and symptoms, the sign or symptom will be reported as an AE and the associated laboratory result or vital sign will be considered as additional information. Wherever possible the reporting Investigator uses the clinical, rather than the laboratory term (eg, anaemia versus low haemoglobin value). In the absence of clinical signs or symptoms, clinically relevant deteriorations in non-mandated parameters should be reported as AE(s).

Any new or aggravated clinically relevant abnormal medical finding at a physical examination as compared with the baseline assessment will be reported as an AE.

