6.4.7.1 Resting 12-lead ECG

Electrocardiograms will be recorded in the supine position after the healthy volunteer has rested in this position for at least 10 minutes. Only the overall evaluation (normal/abnormal) will be captured in the CRF. Any abnormalities (including corrected QT interval [QTc] values) should be reviewed by a cardiologist or an appropriately qualified person.

The original ECG printouts with variables must be signed and dated and stored in the healthy volunteer's medical record as source data.

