6.4.10 Ophthalmology

A full ophthalmologic examination including a slit-lamp funduscopy, best corrected visual acuity, and intraocular pressure measurement must be performed at screening for all volunteers. If a volunteer experiences visual disturbance the ophthalmological algorithm should be followed for diagnosis and management of these symptoms. Volunteers should undergo an ophthalmological examination and Optical Coherence Tomography scans should be considered.

The same ophthalmic expert will perform ophthalmic assessments on each occasion where possible.

During the study the healthy volunteers will be asked to report if they experience any eye symptoms such as dry eyes, grittiness, or irritation. In case of clinically relevant ophthalmological abnormalities, an additional full examination will be performed.

Any corneal changes must be monitored frequently, with therapeutic intervention as appropriate until resolution. Any abnormalities elicited will be recorded as an AE.

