11. EVALUATION AND CALCULATION OF VARIABLES

11.1 Calculation or derivation of efficacy variable(s) (Not applicable)

11.2 Calculation or derivation of safety variable(s)

11.2.1 Other significant adverse events (OAE)

During the evaluation of the AE data, an AstraZeneca medically qualified expert will review the list of AEs that were not reported as SAEs and discontinuation of IP due to AE (DAEs). Based on the expert's judgement, significant AEs of particular clinical importance may, after consultation with the Global Safety Physician, be considered OAEs and reported as such in the CSR. A similar review of laboratory/vital signs/ECG data will be performed for identification of OAEs.

Examples of these are marked haematological and other laboratory abnormalities, and certain events that lead to intervention (other than those already classified as serious), dose reduction or significant additional treatment.

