12.2.3 Safety and tolerability measurements

All safety data (scheduled and unscheduled) will be presented in the data listings. Continuous variables will be summarised using descriptive statistics (n, mean, SD, min, median, max). Categorical variables will be summarised in frequency tables (frequency and proportion). Graphical presentations may be used as appropriate. Examples may include line graphs showing individual or mean development over time, and shift plots showing pre-treatment values on horizontal axis and post-treatment values on vertical axis.

All AEs will be collected for each healthy volunteer from the time of informed consent until Day 7 or the last day of urine/faecal collection (whichever is later). Adverse events that occur before administration will be reported separately.

Adverse events will be summarised by Preferred Term and System Organ Class using MedDRA vocabulary. Furthermore, listings of SAEs and AEs that led to withdrawal will be made and the number of healthy volunteers who had any AEs, SAEs, AEs that led to withdrawal, and AEs with severe intensity will be summarised.

Tabulations and listings of data for vital signs (blood pressure, pulse rate, and body temperature), and clinical laboratory tests will be presented. Where applicable, data will be summarised for the absolute value at each scheduled assessment, and for the corresponding change from baseline. For clinical laboratory tests, listings of values for each healthy volunteer will be presented with abnormal or out-of-range values flagged. Clinical laboratory data will be reported in Système International (SI) units (where available) in the CSR.

Results from the physical examinations, ECGs, echocardiograms, and eye examinations will be presented in listings only.

Extra measurements (such as unscheduled or repeat assessments) will not be included in the descriptive statistics, but will be included in subject listings.

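### Section 6.4.3 keeps non-serious ECG deterioration out of the adverse events because results are summarised in the study report, but ECG values are neither entered in the CRF nor summarised

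*Protocol*

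**What the plan says.** Section 6.4.3 (the part on examinations and tests) first gives a reason: "The results from protocol mandated laboratory tests and vital signs will be summarised in the Clinical Study Report (CSR"). From that it draws a rule: "Deterioration as compared to baseline in protocol-mandated laboratory values, vital signs, ECGs, and other safety assessments should therefore only be reported as AEs" if one of the seriousness criteria is fulfilled. The rule covers ECGs and other safety assessments; the reason names neither.

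For ECGs the other sections say:

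- Section 6.4.7.1, data capture: "Only the overall evaluation (normal/abnormal) will be captured in the CRF". The printouts with their variables are signed, dated and kept in the medical record as source data.
- Section 6.4.7.1, review: "Any abnormalities (including corrected QT interval [QTc] values) should be reviewed by a cardiologist or an appropriately qualified person".
- Section 12.2.3, reporting: "Results from the physical examinations, ECGs, echocardiograms, and eye examinations will be presented in listings only". Vital signs and laboratory tests, by contrast, are tabulated, with change from baseline where applicable.
- Section 11.2.1, sponsor review: "A similar review of laboratory/vital signs/ECG data will be performed for identification of OAEs".
- Section 6.4.1, general definition: an adverse event can be "the abnormal results of an investigation (eg, laboratory findings, ECG").
- Section 6.4.10, eye examinations: "Any abnormalities elicited will be recorded as an AE".

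The synopsis lists the electrocardiogram among the safety outcome variables, and secondary objective 4 is safety and tolerability. Table 2 schedules ECGs at screening, Day -1, Day 1 and Day 7. The final assessment described in section 6.2.2 does not mention an ECG.

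**The concern.** Leaving non-serious test changes out of the adverse events is a sound convention when the test results are reported in another form. Section 6.4.3 states that condition itself and then applies the rule to a test that does not meet it. Laboratory values and vital signs go into tables as numbers. An ECG goes into a listing as one word.

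Two kinds of change can then drop out of every planned output: one that stays within normal, and one in a tracing already called abnormal. The second is possible under the entry criteria, because exclusion 11 bars only ECG abnormalities judged clinically important and the volunteers are 50 to 65 years old. How often it would occur cannot be told from the protocol.

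At stake is what the report can say about a stated safety outcome. Section 1.3.1 describes a previous healthy-volunteer study as showing no clinically important trends in ECG parameters. This study would hold no ECG parameters in its database from which to make the same statement.

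**Working it through.** The plan gives no figure to reproduce on this point. The check traces a non-serious, asymptomatic ECG change through each place where it could be recorded, and then counts the ECGs concerned.

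**Trace**

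| Place | Normal to abnormal | Change within normal | Worsening of an abnormal ECG |
|---|---|---|---|
| Adverse event record (6.4.3) | No | No | No |
| CRF entry (6.4.7.1) | Visible | Not visible | Not visible |
| Listing in the report (12.2.3) | Visible | Not visible | Not visible |
| Summary or change from baseline (12.2.3) | None planned | None planned | None planned |
| Printout in the medical record (6.4.7.1) | Yes | Yes | Yes |
| Review by a qualified person (6.4.7.1) | Yes | Only if judged an abnormality | Yes |
| Sponsor review for other significant events (11.2.1) | Yes | CRF shows no change | CRF shows no change |

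The last two columns are the gap. The change is on paper at the site, and a qualified person may have looked at it, but no planned field or output carries it into the report.

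**Does the stated reason cover ECGs?** The premise in section 6.4.3 is a summary in the report, for laboratory tests and vital signs. Section 12.2.3 plans exactly that for those two and places ECGs under listings. The step from premise to rule therefore fails for ECGs on the protocol's own text. Section 6.4.1 also names an abnormal ECG as a possible adverse event, so the general definition and the restriction pull in different directions.

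**Number of ECGs**

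- Volunteers: 6 (synopsis). Scheduled ECGs each: 4 (Table 2).
- All scheduled ECGs: 6 × 4 = 24.
- Certainly pre-dose (screening and Day -1): 6 × 2 = 12.
- Post-dose at most (Day 1 and Day 7): 24 − 12 = 12.
- Table 2 gives the day but no hour for the Day 1 ECG, and section 6 allows pre-dose assessments in the hour before dosing. If the Day 1 ECG is taken pre-dose, the post-dose count is 6 × 1 = 6.

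So between 6 and 12 recordings can show a post-dose change. The pre-dose recordings matter only as baseline.

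**The case against.** The best defence is that this is a single-dose, descriptive mass-balance study in 6 men, with several safeguards for ECGs. Each evaluation is in the CRF and is listed by volunteer. Printouts are kept and abnormalities are reviewed. The sponsor's expert reviews ECG data, a term that section 11.2.1 does not confine to CRF entries, and section 9.3 gives the sponsor's representative access to original records. Symptoms are adverse events in any case, and a marked asymptomatic change could qualify as serious under the medically important event criterion in section 6.4.2. Section 1.3.1 names no QT or conduction risk for healthy volunteers.

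Much of this stands. At this sample size listings in place of summaries are no defect in themselves. It does not repair the reasoning in section 6.4.3, and the listing cannot stand in for a summary when it holds no values.

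A reader might infer more than the protocol supports:

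- *That a non-serious ECG change is recorded nowhere, or that the ECG data can show no change.* The normal/abnormal entry, the listing and the printouts contradict this; a shift from normal to abnormal can be read directly.
- *That a fall in ejection fraction is lost in the same way.* After screening, echocardiograms are done only for cause, following a cardiac event that may itself be an adverse event. They are arguably non-mandated, and section 6.4.3 makes clinically relevant deterioration in non-mandated parameters reportable.
- *That section 6.4.10 flatly contradicts section 6.4.3.* Post-screening eye examinations are likewise for cause, and a specific rule can stand beside a general one. The wording needs reconciling, no more.
- *That no post-dose ECG need be taken, because section 6.2.2 omits it.* Section 6.4.7 takes ECG timing from Table 2, which marks Day 7. The omission is an inconsistency to correct.
- *That Table 3 provides for no ECG.* The table's columns cannot be read reliably in the available text, so nothing is concluded from it.

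**Conclusion.** The point holds in a limited form. The exemption in section 6.4.3 rests on a summary that the protocol does not plan for ECGs, and only a binary evaluation reaches the database. A non-serious, asymptomatic ECG change within a category is consequently neither an adverse event nor a planned result, although ECG is a listed safety outcome and the protocol's own definition admits an abnormal ECG as an adverse event.

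The size is modest: 6 to 12 post-dose recordings, and only changes that do not cross from normal to abnormal. The primary objective is untouched. The conclusion assumes that the CRF follows section 6.4.7.1 as written. A statistical analysis plan could add ECG tables, but it could not tabulate intervals that the study does not capture.

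**What to change.** 1. In section 6.4.7.1, enter heart rate, PR, QRS, QT and QTcF in the CRF from the printouts already required.
2. In section 12.2.3, list these values with change from baseline. A summary table is optional with 6 volunteers.
3. In section 6.4.3, limit the exemption for non-serious changes to laboratory values and vital signs, the results that are in fact summarised, so that clinically relevant ECG deterioration is recorded as an adverse event. Align the wording with sections 6.4.1 and 6.4.10.
4. Reconcile section 6.2.2, which omits the ECG, with Table 2, which schedules one on Day 7.

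The cost is a wording change, an added CRF page and transcription of 24 sets of values. No new procedure or sample is needed. The downside is slightly more data entry and possibly one or two more reported adverse events.

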6.4.4 Reporting of serious adverse events

All SAEs have to be reported, whether or not considered causally related to the IP, or to the study procedure(s). All SAEs will be recorded in the CRF.

If any SAE occurs in the course of the study, then Investigators or other study centre staff inform appropriate AstraZeneca representatives immediately, or **no later than 24 hours** of when he or she becomes aware of it.

The designated AstraZeneca representative works with the Investigator to ensure that all the necessary information is provided to the AstraZeneca Patient Safety data entry site **within 1 calendar day** of initial receipt for fatal and life threatening events **and within 5 calendar days** of initial receipt for all other SAEs.

For fatal or life-threatening AEs where important or relevant information is missing, active follow-up is undertaken immediately. Investigators or other study centre staff inform AstraZeneca representatives of any follow-up information on a previously reported SAE immediately, or **no later than 24 hours** of when he or she becomes aware of it.

Investigators or other study centre staff send relevant CRF modules by fax to the designated AstraZeneca representative.

The reference document for definition of expectedness/listedness is the Investigator's Brochure for the AstraZeneca drug.

6.4.5 Laboratory safety assessment

Blood and urine samples for determination of clinical chemistry, haematology, and urinalysis will be collected at the time points indicated in the Study Plan (see [Table 2](#) and [Table 3](#)).

The following laboratory variables will be measured:

Table 5 Laboratory safety variables

Haematology^a	Clinical Chemistry^a	Virology	Urinalysis^b	Drugs of Abuse
Basophils	Alanine Aminotransferase (ALT)	Hepatitis B Surface Antigen	Bilirubin	Amphetamines
Eosinophils	Albumin	Hepatitis C Antibody	Blood	Barbiturates
Haematocrit (Packed Cell Volume- PCV)	Alkaline Phosphatase	Human Immunodeficiency Virus (HIV) Antibody	Glucose	Benzodiazepines
Haemoglobin	Aspartate Aminotransferase (AST)		Ketones	Cocaine
Lymphocytes	Bicarbonate		Leukocytes	Marijuana/Cannabis.
Mean Cell Haemoglobin (MCH)	Bilirubin (Total)		Nitrates	Methadone
Mean Cell Haemoglobin Concentration (MCHC)	Bilirubin (Direct) (only if Total is elevated)		pH	Methamphetamine
Mean Cell Volume (MCV)	Calcium		Protein	Ecstasy
Monocytes	Chloride		Specific gravity	Morphine/Opiates
Neutrophils	Creatinine		Urobilinogen	Phencyclidine

Haematology^a	Clinical Chemistry^a	Virology	Urinalysis^b	Drugs of Abuse
Platelet Count	Gamma Glutamyl Transpeptidase (GGT)			Tricyclic Antidepressants
Red Blood Cell (RBC) Count	Glucose (Fasting)			
White Blood Cell (WBC) Count	Potassium			
	Phosphate (Inorganic)			
	Protein (Total)			
	Sodium			
	Urea			

^a The healthy volunteers will be fasted for 4 hours prior to any clinical laboratory evaluations.

^b Urinalysis to be performed by standard dipstick analysis. Microscopy should only be performed if the urinalysis shows a positive result.

Blood will be tested for hepatitis B surface antigen, antibodies to hepatitis C, and antibodies to HIV at screening. CRCL will be calculated at screening using the Cockcroft-Gault formula.

Urine will be tested at screening and on Day -1 for drugs of abuse. Urine will be collected at the study centre. Alcohol will be assessed by an alcohol breath test. Smoking will be assessed by performing a breath carbon monoxide test. If a volunteer tests positive for drugs of abuse, a retest may be performed and the volunteer may be excluded from entering the study, as judged by the Investigator.

Laboratory values outside the reference limit suspected to be of any clinical significance will be repeated. Volunteers in whom suspected clinical significance is confirmed will either not be included or if already enrolled will be followed until normalisation or for as long as the Investigator considers necessary. Additional laboratory variables may be performed for safety reasons if judged appropriate by the Investigator. Further details are provided in the Laboratory Manual.

The safety laboratory samples will be analysed using routine methods at

NB. In case a healthy volunteer shows an AST or ALT ≥ 3 x ULN or total bilirubin ≥ 2 x ULN please refer to [Appendix D](#) 'Actions required in cases of combined increase of Aminotransferase and Total Bilirubin – Hy's Law', for further instructions.

For blood volume see Section [7.1](#).

6.4.6 Physical examination

Physical examinations will be performed at the time points indicated in [Table 2](#).

A complete physical examination will be performed during screening and on Day 7. This examination will include an assessment of the following: general appearance, respiratory, cardiovascular, abdomen skin, head and neck (including ears, eyes, nose, and throat), lymph nodes, thyroid, abdomen, musculo-skeletal (including spine and extremities), and neurological systems. On Day -1 only a brief physical examination is required (including general appearance, skin, abdomen, cardiovascular system, and lungs).

6.4.7 ECG

The ECG assessments will be performed at the time points indicated in [Table 2](#).

6.4.7.1 Resting 12-lead ECG

Electrocardiograms will be recorded in the supine position after the healthy volunteer has rested in this position for at least 10 minutes. Only the overall evaluation (normal/abnormal) will be captured in the CRF. Any abnormalities (including corrected QT interval [QTc] values) should be reviewed by a cardiologist or an appropriately qualified person.

The original ECG printouts with variables must be signed and dated and stored in the healthy volunteer's medical record as source data.

6.4.8 Echocardiogram

Echocardiogram will be performed at screening to determine LVEF.

A complete high quality standardised 2-D with Doppler echocardiographic examinations should be performed by an experienced sonographer (preferably with the same sonographer performing all echocardiograms for a given volunteer) including evaluation of both systolic and diastolic function. Ejection fraction determinations should be determined quantitatively based on bi-plane measurements of end diastolic and end systolic left ventricular volumes.

6.4.9 Vital signs

Vital signs assessments will be performed at the times indicated in [Table 2](#).

6.4.9.1 Pulse and blood pressure

Supine blood pressure and pulse rate will be measured using standard equipment after 10 minutes rest on a bed. Additional blood pressure/pulse assessments may be taken for safety at the discretion of the Investigator or delegate.

6.4.9.2 Height and weight

Height (cm) and weight (kg) will be evaluated at screening and BMI (kg/m^2) will be calculated. Only weight will be evaluated at Day -1 and on Day 7. The healthy volunteers will be required to remove their shoes and wear light indoor clothing for these measurements. When requested or judged necessary for the program, body weight and/or BMI can be measured at additional time points.

6.4.9.3 Body temperature

Body temperature will be measured in degrees Celsius using an automated thermometer at the times indicated in the Study Plan (see [Table 2](#)).

6.4.10 Ophthalmology

A full ophthalmologic examination including a slit-lamp funduscopy, best corrected visual acuity, and intraocular pressure measurement must be performed at screening for all volunteers. If a volunteer experiences visual disturbance the ophthalmological algorithm should be followed for diagnosis and management of these symptoms. Volunteers should undergo an ophthalmological examination and Optical Coherence Tomography scans should be considered.

The same ophthalmic expert will perform ophthalmic assessments on each occasion where possible.

During the study the healthy volunteers will be asked to report if they experience any eye symptoms such as dry eyes, grittiness, or irritation. In case of clinically relevant ophthalmological abnormalities, an additional full examination will be performed.

Any corneal changes must be monitored frequently, with therapeutic intervention as appropriate until resolution. Any abnormalities elicited will be recorded as an AE.

